3.1 Study Endpoints

Definitions of baseline, primary, secondary and exploratory endpoints are defined in this section. Where Sleep Diary endpoints are described, the time points refer to the mean of the final 7 nights before the visit unless otherwise stated.

3.1.1 Primary Endpoint

The primary endpoint is the mean change from Study Baseline in sSOL at Month 6.

3.1.2 Secondary Endpoints

The key secondary endpoints are:

- Mean change from Study Baseline in sSE at Month 6

- Mean change from Study Baseline of sWASO at Month 6

Additional secondary endpoints are:

- Mean change from Study Baseline of sSOL, of sSE, of sWASO and of sTST, at the beginning of treatment (mean of the 7 nights after the 1st dose in Period 1), at Month 1 and at Month 3
- Mean change from Study Baseline of sTST at Month 6
- Proportion of responders at Month 6 and Month 12, where sleep onset responder is defined as follows: sSOL at Study Baseline is ≥ 30 minutes and mean sSOL at 6 months is ≤ 20 minutes, and sleep maintenance responder is defined as follows: sWASO at Study Baseline is ≥ 60 minutes and mean sWASO at 6 months is ≤ 60 minutes and shows a reduction of >10 minutes compared to Study Baseline.
- Change from Study Baseline in daytime functioning, assessed as the total score from the 4 items on daytime functioning, on the ISI, at Months 1, 3, and 6
- Change from Study Baseline on the FSS at Months 1, 3, and 6
- Ratings on the morning sleepiness item of the Sleep Diary, for:
 - The mean change from Study Baseline of the 1st 7 mornings after the 1st dose in Period 1 and Period 2
 - The mean change from Study Baseline at: Month 1, Month 3, and Month 6
 - The mean change from Study Baseline and from Treatment Period 2 Baseline (as appropriate): for subjects with 1, 3, 6, 9 and 12 months exposure
 - The mean change from Screening for the 1st 7 mornings and 2nd 7 mornings of the Follow-up Period
- Rebound insomnia endpoints as assessed from the Sleep Diary during the Follow-up Period
 - Change from Screening of sSOL on each of the 1st 3 nights, mean sSOL of the 1st 7 nights, and mean sSOL of the 2nd 7 nights of the Follow-up Period
 - Change from Screening of sWASO on each of the 1st 3 nights, mean sWASO of the 1st 7 nights and mean sWASO of the 2nd 7 nights of the Follow-up Period
 - Proportion of subjects whose sSOL is longer than at Screening for each of the 1st 3 nights, or whose mean sSOL is longer than at Screening for 1st 7 nights or 2nd 7 nights of the Follow-up Period
 - Proportion of subjects whose sWASO is higher than at Screening for each of the 1st 3 nights, or whose mean sWASO is higher than at Study Baseline for the 1st 7 nights or 2nd 7 nights of the Follow-up Period
- Persistence of Effect
 - Mean change from Study Baseline of sSOL, of sSE, of sWASO and of sTST at Months 3, 6, 9, and 12 compared to Month 1
 - Mean change from Treatment Period 2 Baseline (Month 6) of sSOL, of sSE, of sWASO and of sTST at Months 9 and 12 compared to Month 7 (the 1st month of treatment in Period 2)

- Mean change from Study Baseline and Treatment Period 2 Baseline (as appropriate) of sSOL, of sSE, of sWASO and of sTST at 3 and 6 months exposure compared to 1 month of exposure

Safety and Tolerability of Lemborexant

- During Period 1, compared to PBO
- For subjects exposed to lemborexant for 3, 6, 9, and 12

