- Proportion of responders at Month 6 and Month 12, where sleep onset responder is defined as follows: sSOL at Study Baseline is ≥ 30 minutes and mean sSOL at 6 months is ≤ 20 minutes, and sleep maintenance responder is defined as follows: sWASO at Study Baseline is ≥ 60 minutes and mean sWASO at 6 months is ≤ 60 minutes and shows a reduction of >10 minutes compared to Study Baseline.
- Change from Study Baseline in daytime functioning, assessed as the total score from the 4 items on daytime functioning, on the ISI, at Months 1, 3, and 6
- Change from Study Baseline on the FSS at Months 1, 3, and 6
- Ratings on the morning sleepiness item of the Sleep Diary, for:
 - The mean change from Study Baseline of the 1st 7 mornings after the 1st dose in Period 1 and Period 2
 - The mean change from Study Baseline at: Month 1, Month 3, and Month 6
 - The mean change from Study Baseline and from Period 2 Baseline (as appropriate) for subjects with 1, 3, 6, 9, and 12 months exposure (revised per Amendment 06)
 - The mean change from Screening for the 1st 7 mornings and 2nd 7 mornings of the Follow-up Period
- Rebound insomnia endpoints as assessed from the Sleep Diary during the Follow-up Period (revised per Amendment 02)
 - Change from Screening of sSOL on each of the 1st 3 nights, mean sSOL of the 1st 7 nights, and mean sSOL of the 2nd 7 nights of the Follow-up Period
 - Change from Screening of sWASO on each of the 1st 3 nights, mean sWASO of the 1st 7 nights and mean sWASO of the 2nd 7 nights of the Follow-up Period
 - Proportion of subjects whose sSOL is longer than at Screening for each of the 1st 3 nights, or whose mean sSOL is longer than at Screening for 1st 7 nights or 2nd 7 nights of the Follow-up Period
 - Proportion of subjects whose sWASO is higher than at Screening for each of the 1st 3 nights, or whose mean sWASO is higher than at Screening for the 1st 7 nights or 2nd 7 nights of the Follow-up Period

- Persistence of Effect
 - Mean change from Study Baseline of sSOL, of sSE, of sWASO and of sTST at Months 3, 6, 9, and 12 compared to Month 1
 - Mean change from Treatment Period 2 Baseline (Month 6) of sSOL, sSE, sWASO, and sTST at Months 9 and 12 compared to Month 7 (the first month of treatment in Period 2) (revised per Amendment 06)
 - Mean change from Study Baseline and Treatment Period 2 Baseline (as appropriate) of sSOL, sSE, sWASO, and sTST at 3 and 6 months exposure compared to 1 month of exposure (revised per Amendment 06)

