9.7.1.6.2 SECONDARY EFFICACY AND PHARMACODYNAMIC ANALYSES

Key Secondary Efficacy Analyses (revised per Amendment 03)

The change from Study Baseline of key secondary endpoints sSE and sWASO at Month 6 comparing LEM5 and LEM10 to PBO will be analyzed using the same analysis method as the primary endpoint. The missing values will be imputed using a pattern mixture model utilizing MI assuming MNAR. The treatment comparison will be performed using contrasts. The p-value, LS means and the 95% confidence interval (CI) of the treatment differences will also be provided. (revised per Amendment 03)

Other Secondary Efficacy Analyses (revised per Amendment 03)

The other secondary efficacy endpoints (change from Study Baseline of the following for LEM5 and LEM10 compared to PBO; mean sSOL, mean sSE, mean sWASO and mean sTST at 1st 7 nights, Months 1 and 3; and mean sTST at Month 6; ISI total of 4 items of daytime functioning at Months 1, 3, and 6, and FSS score at Months 1, 3, and 6) will be analyzed using MMRM, assuming MAR. The FSS will also be analyzed for responders, including only those subjects who endorsed clinically significant fatigue at Study Baseline. (revised per Amendments 03 and 06)

The proportion of responders, separately for sSOL and sWASO, will be analyzed using the Cochran-Mantel-Haenszel test, adjusted for country and age group, after the 1st 7 nights and for the last 7 nights of treatment at the end of Months 1, 3, 6 and 12, for LEM5 and LEM10 compared to PBO.

Rebound insomnia is defined as worsened sleep relative to Screening after study drug treatment is completed. Sleep Diary data from the Follow-up Period will be compared to Sleep Diary data from the Screening Period to assess whether subjects experience rebound

insomnia. Specifically, a higher value for sSOL or sWASO during the Follow-up Period compared to the mean sSOL or sWASO value during the Screening Period will be considered worsened sleep.

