To assess rebound insomnia, both categorical analysis at the subject level and continuous analysis at the group mean level will be performed. For each of the first 3 nights and each of the 2 weeks of the Follow-up Period the proportion of subjects whose corresponding value for sSOL or sWASO exceeds the corresponding Screening Period value by 5 minutes will be summarized by treatment group and compared to placebo. The percentage of ‘rebounders’ between each treatment and placebo group will be analyzed using a Cochran-Mantel-Haenszel test, adjusted for country and age group.

To assess statistical significance using the continuous data at the group mean level, the data will be analyzed using ANCOVA, adjusted for country, age group and treatment. The LS mean of each of the first 3 nights and each week of the Follow-up Period will be compared to the Screening Period between each treatment group and placebo. If the lower bound of the 95% CI of sSOL or sWASO for each of the first 3 nights and the mean of each week of the Follow-Up Period exceeds the upper bound of a 95% CI for the values during the Screening Period in the given treatment group, it will be considered strong evidence for rebound insomnia. If the LS means for sSOL and sWASO for the Follow-up Period are all lower than for the Screening Period, then no rebound insomnia is suggested. Otherwise, the degree to which the parameters worsen, and the time point(s) at which they worsen will be considered to evaluate whether clinically meaningful rebound insomnia is present.

To evaluate morning sleepiness item on the Sleep Diary, the mean change from Study Baseline of the 1st 7 mornings after the 1st dose in Period 1, Month 1, Month 3 and Month 6 will be analyzed using MMRM, assuming MAR. Additionally, morning sleepiness change from both Study Baseline and Period 2 Baseline for the 1st 7 mornings after the 1st dose in Period 2, Month 9, and Month 12, and also the change from Screening of each of the 2 weeks of the Follow-Up Period will be summarized with mean and 95% CI's. (revised per Amendment 03)

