 - The sleep onset responder is defined as: sSOL at Study Baseline (or Period 2 Baseline) is >30 minutes and mean sSOL at each month (Months 7, 8, 9, 10, 11 and 12) is ≤ 20 minutes,
 - The sleep maintenance responder is defined as: sWASO at Study Baseline (or Period 2 Baseline) is >60 minutes and mean sWASO at each month (Months 7, 8, 9, 10, 11

and 12) is ≤ 60 minutes and shows a reduction of >10 minutes compared to Study Baseline (or Period 2 Baseline).

The proportion of responders will be analyzed based on the subjects with sSOL > 30 minutes at the baseline for sSOL and separately the subjects with sWASO > 60 minutes at the baseline for sWASO.

- Morning sleepiness item of the Sleep Diary:
 - Change from Study Baseline of mean rating on morning sleepiness at the 1st 7 mornings after the 1st dose in Treatment Period 1, Month 1, Month 2, Month 3, Month 4, Month 5 and Month 6.
 - Change of mean rating on morning sleepiness from Study Baseline / Treatment Period 2 Baseline for 1st 7 mornings after the 1st LEM dose, 1, 3, 6, 9 and 12 months of exposure to LEM5 and LEM10. Data from subjects randomized to LEM5 or LEM10 at the start of the study will use Study Baseline, data from subjects who were re-randomized to LEM5 or LEM10 in Period 2 will use Treatment Period 2 Baseline. Change from Screening of mean rating on morning sleepiness of 1st 7 mornings and 2nd 7 mornings in Follow-Up Period.
- Rebound insomnia endpoints during the Follow-up Period as follows:
 - Change from Screening of sSOL on each of the 1st 3 nights, mean sSOL of the 1st 3 nights, mean sSOL of the 1st 7 nights, and mean sSOL of the 2nd 7 nights of the Follow-up Period
 - Change from Screening of sWASO on each of the 1st 3 nights, mean sWASO of the 1st 3 nights, mean sWASO of the 1st 7 nights and mean sWASO of the 2nd 7 nights of the Follow-up Period
 - Proportion of subjects whose sSOL is longer than at Screening by at least 5 minutes for each of the 1st 3 nights, mean sSOL of the 1st 3 nights, mean of the 1st 7 nights, and mean of the 2nd 7 nights of the Follow-up Period
 - Proportion of subjects whose sWASO is higher than at Screening by at least 5 minutes for each of the 1st 3 nights, mean sWASO of the 1st 3 nights, mean of the 1st 7 nights, and mean of the 2nd 7 nights of the Follow-up Period.

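### The subject-level rebound endpoint is stated with two thresholds and, for the weekly sWASO means only, with two reference periods

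*SAP*

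**What the plan says.** **Definition.** Protocol 9.7.1.6.2, with matching synopsis text, states: "Rebound insomnia is defined as worsened sleep relative to Screening after study drug treatment is completed". It then treats any value above the subject's Screening Period mean as worsened sleep.

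**Endpoint lists.** SAP 3.1.2 counts, for sSOL, subjects "whose mean sSOL is longer than at Screening for 1st 7 nights or 2nd 7 nights of the Follow-up Period". For sWASO it begins "Proportion of subjects whose sWASO is higher than at Screening for each of the 1st 3 nights" and ends "or whose mean sWASO is higher than at Study Baseline for the 1st 7 nights or 2nd 7 nights of the Follow-up Period". Protocol 9.7.1.1.2 carries the same wording. The protocol synopsis instead ends the sWASO item "or whose mean sWASO is higher than at Screening for the 1st 7 nights or 2nd 7 nights of the Follow-up Period".

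**Analysis text.** The categorical analysis in protocol 9.7.1.6.2 and in the synopsis counts a subject whose value "exceeds the corresponding Screening Period value by 5 minutes". SAP 3.4.2.4 gives "Proportion of subjects whose sSOL is longer than at Screening by at least 5 minutes for each of the 1st 3 nights" and "Proportion of subjects whose sWASO is higher than at Screening by at least 5 minutes for each of the 1st 3 nights", and applies the same reference and margin to the mean of the first three nights and to both weekly means.

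**Study Baseline.** SAP 6.1.1 sets it, for diary parameters, as the mean of the last 7 mornings before Visit 3a in the Run-In Period. Protocol 9.2.2 puts all subjects on single-blind placebo during that period.

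**Group-level analysis.** The ANCOVA in SAP 3.4.2.4 lists baseline and the last seven follow-up nights among its time points. The rule that follows compares confidence limits for the second seven nights with those for the Screening Period.

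**The concern.** Rebound is a stated secondary objective, and protocol 9.5.3 calls it a safety-related assessment. A subject whose sSOL is 3 minutes above Screening counts under the endpoint lists and does not count under the analysis text. For weekly sWASO, a programmer who follows SAP 3.1.2 literally would compare follow-up with a week on placebo, not with the untreated state from which rebound is defined. Protocol 9.2.2 expects large placebo effects in insomnia trials. If sleep improves on run-in, that reference is lower and more subjects are counted.

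The absolute proportion matters because subjects who finish Period 2 are all on LEM5 or LEM10. SAP 3 itself notes that Period 2 has no placebo control group, so a shift caused by the definition is not offset by a concurrent comparison.

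**Working it through.** **1. References and margins side by side**

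| Place | sSOL | sWASO, single nights | sWASO, weekly means | Margin |
|---|---|---|---|---|
| Protocol synopsis, endpoint list | Screening | Screening | Screening | any increase |
| Protocol 9.7.1.1.2 | Screening | Screening | Study Baseline | any increase |
| SAP 3.1.2 | Screening | Screening | Study Baseline | any increase |
| Protocol synopsis and 9.7.1.6.2, categorical analysis | Screening | Screening | Screening | exceeded by 5 min |
| SAP 3.4.2.4 | Screening | Screening | Screening | at least 5 min |

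The threshold conflict covers both parameters and all windows. The reference conflict covers one cell in each of two lists. The two 5-minute wordings differ only at exactly 5 minutes.

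**2. Second-week window**

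Protocol 9.1.2.4 places the End of Study visit 14 to 18 days after treatment. With n follow-up nights, the last seven are nights n−6 to n and the second seven are nights 8 to 14.
- n = 14: the same nights.
- n = 15: nights 9–15, of which six are shared.
- n = 18: nights 12–18, of which three are shared (12, 13 and 14).

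SAP 6.1.2 has a rule only for the case where the first and last seven nights overlap, so it does not settle 15 to 18 nights.

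**3. Size of the threshold effect (illustration)**

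The documents give no rebound proportion, so there is no plan figure to reproduce. The inputs are the SDs of change in SAP 2: 33 min for sSOL and 43 min for sWASO. They reproduce the plan's power at 300 per group, using Φ(δ / (SD·√(2/300)) − 1.96):
- sWASO: 11.4 / 3.511 − 1.96 = 1.287, giving 90.1% (stated 90%).
- sSOL: 8.7 / 2.694 − 1.96 = 1.269, giving 89.8% (stated above 90%).

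Now let D, follow-up minus Screening, be Normal(m, SD). The proportion above a margin t is 1 − Φ((t − m)/SD).
- sSOL, m = 0: t = 0 gives 50.0%; t = 5 gives 1 − Φ(5/33) = 44.0%.
- sWASO, m = 0: t = 0 gives 50.0%; t = 5 gives 1 − Φ(5/43) = 45.4%.

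| m (min) | sSOL any / ≥5 min | sWASO any / ≥5 min |
|---|---|---|
| −30 | 18.2% / 14.4% | 24.3% / 20.8% |
| −20 | 27.2% / 22.4% | 32.1% / 28.0% |
| −10 | 38.1% / 32.5% | 40.8% / 36.4% |
| 0 | 50.0% / 44.0% | 50.0% / 45.4% |

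The threshold alone is worth 3.7 to 6.0 points for sSOL and 3.5 to 4.6 points for sWASO.

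**4. Weekly sWASO against Study Baseline (conditional)**

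Suppose run-in sWASO lies x minutes below Screening, with the same SD. Any increase over Study Baseline then has probability 1 − Φ(−(m + x)/43). The excess over the SAP 3.4.2.4 rule, for m from −30 to 0, is:
- x = 0: 3.5 to 4.6 points (the threshold effect alone)
- x = 5: 7.3 to 9.3 points
- x = 10: 11.3 to 13.8 points
- x = 20: 20.0 to 22.8 points

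The documents give no value for x. If run-in were 5 minutes above Screening (x = −5), the two rules would agree.

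**The case against.** The best reply is that the intended rule can be read. The term rebounder appears only in the protocol's analysis text, with Screening and 5 minutes, and SAP 3.4.2.4 applies Screening and at least 5 minutes to every parameter and window. The general definition of worsened sleep can be taken as the concept, with the cut-off as its subject-level form. Study Baseline looks like a drafting slip present in protocol 9.7.1.1.2 and SAP 3.1.2. Most of this stands. It does not remove the point: SAP 3.1 says that the endpoints are defined in that section, nothing gives 3.4.2.4 precedence, and following 3.1.2 literally yields a different weekly sWASO proportion that contradicts the definition of rebound.

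The stakes are also limited. SAP 3.4 rules out hypothesis tests for efficacy endpoints beyond Month 6, and the criterion for strong evidence of rebound is the group-level comparison of confidence limits, which does not use the subject-level margin.

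A reader might go further and infer any of the following, none of which the documents support:
- **That the reference conflict runs through the whole rebound endpoint.** It is confined to the weekly sWASO means.
- **That definitions alone move the result by about 9 points.** That figure combines both conflicts and needs an assumed 5-minute fall from Screening to run-in.
- **That no Screening reference exists.** SAP 6.1.1 gives no Screening diary mean, but protocol 9.7.1.6.2 and the synopsis name the mean over the Screening Period.

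**Conclusion.** The inconsistency is real and is in the current text of both documents. It consists of a threshold conflict for all subject-level rebound proportions, a reference conflict for the weekly sWASO means only, and a mismatch of reference and second-week window in the SAP 3.4.2.4 ANCOVA text. It is more than clerical, because it leaves a reported secondary proportion open to more than one value, but it is modest.

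With mean change 0 the threshold is worth about 6.0 points for sSOL and 4.6 points for sWASO. These sizes rest on normality, although the SAP calls sSOL non-normal, and on SDs for change from Study Baseline at Days 8 to 15 of the dose-finding study across 1 to 25 mg, not for follow-up minus Screening. Single-night values would vary more. The further shift for weekly sWASO cannot be sized from the documents. The primary and key secondary tests at Month 6 do not use any of this text.

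**What to change.** - **Threshold:** adopt the SAP 3.4.2.4 rule, at least 5 minutes above the subject's Screening Period mean, in the protocol synopsis (endpoint list and categorical analysis), protocol 9.7.1.1.2, protocol 9.7.1.6.2 and SAP 3.1.2.
- **Reference:** replace Study Baseline with Screening for the weekly sWASO means in protocol 9.7.1.1.2 and SAP 3.1.2. Keep the Screening Period mean already named in the protocol; narrowing it to the seven mornings before Visit 2a would be a new choice, not a correction.
- **ANCOVA text in SAP 3.4.2.4:** replace baseline with Screening as the modelled reference time point, and the last seven nights with the second seven nights (nights 8–14).
- **SAP 6.1.2:** align its follow-up window wording with nights 8–14.

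The cost is wording in the two documents and matching derivation specifications. No new data are needed.

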3.1.3 Exploratory Endpoints

The following endpoints will be explored for LEM5 and LEM10. Except for PK endpoints, comparisons to PBO will be made.

- Change from Study Baseline in the mean value of the item on quality of sleep from the Sleep Diary for:
 - The 1st 7 mornings after the 1st dose in Period 1
 - Months 1, 3, and 6
- Change from Study Baseline and Treatment Period 2 Baseline (as appropriate) in the mean value of the item on quality of sleep from the Sleep Diary for:
 - subjects with 1, 3, 6, 9 and 12 months exposure
- Change from Study Baseline in:
 - EQ-5D-3L at Months 1, 3, and 6
 - WPAI-GH at Months 3 and 6
- Change from Study Baseline and Treatment Period 2 Baseline (as appropriate) in:
 - EQ-5D-3L for subjects with 3, 6, 9 and 12 months exposure to lemborexant
 - WPAI-GH for subjects with 3, 6, 9 and 12 months exposure to lemborexant
- Number and percentage of subjects with a rating of a positive medication effect on each PGI-Insomnia item (1) at Months 1, 3, and 6 (placebo-controlled Treatment Period 1) and (2) with 3, 6, 9 and 12 months exposure
- Change from Study Baseline and Treatment Period 2 Baseline (as appropriate) of sSOL, sSE, sWASO and sTST with 1, 3, 6, 9 and 12 months exposure, ISI, and FSS with 3, 6, 9 and 12 months exposure
- Mean score on the T-BWSQ of LEM5, and LEM10 compared to PBO at End of Study
- Plasma concentrations of lemborexant and its metabolites M4, M9, and M10
- PK of lemborexant using population modeling
- Relationships between lemborexant PK, efficacy, and/or safety variables using PK/PD modeling

3.1.4 Other Endpoints

Additional endpoints may be further explored on an exploratory or post-hoc basis to facilitate interpretation of study results.

3.2 Study Subjects

3.2.1 Definitions of Analysis Sets

Safety Analysis Set: The Safety Analysis Set is the group of subjects who received at least 1 dose of randomized study drug and had at least 1 postdose safety assessment.

On-Treatment Safety Analysis Set: On-Treatment Safety Analysis Set is the group of subjects who received at least 1 dose of lemborexant and had at least 1 post dose safety assessment.

Full Analysis Set (FAS): The FAS is the group of randomized subjects who received at least 1 dose of randomized study drug and had at least 1 postdose primary efficacy measurement.

On-Treatment Full Analysis Set (FAS): On-Treatment FAS is the group of subjects who received at least 1 dose of lemborexant and had at least 1 post dose primary efficacy measurement.

6-Month Completer Analysis Set: The 6-Month Completer Analysis Set is the group of subjects in the FAS who had all efficacy assessments up to and including Month 6 (ie, Week 1 and Months 1 to 6 visits) without missing primary or key secondary efficacy assessments at any of these visits.

PK Analysis Set: The PK Analysis Set is the group of subjects who have at least 1 quantifiable lemborexant plasma concentration or its metabolites, with adequately documented dosing history.

PK/PD Analysis Set: The PK/PD Analysis Set is the group of subjects receiving either lemborexant or PBO who have efficacy or safety data with documented dosing history. In addition, subjects receiving lemborexant should have at least 1 quantifiable lemborexant concentration data point as per the PK Analysis Set.

Per Protocol Analysis Set (PP): The PP is the group of subjects who sufficiently complied with the protocol. This analysis set will include all subjects in the Full Analysis Set who sufficiently complied with the protocol during Period 1. The criteria for exclusion in this analysis set are listed below:

- Violated inclusion/exclusion criteria
- Duplicate randomization
- Missing primary efficacy assessment
- Prohibited concomitant medication

- Study drug not administered
- Incorrect study drug kit dispensed
- Non compliance of study medication

Subjects who met any of the criteria listed above will be excluded from the PP due to possible introduction of bias.

The number and percentage of subjects in each analysis set will be summarized by treatment groups using descriptive statistics. The summaries for FAS and PP will be based on subjects “as randomized”. The summary for Safety Analysis Set will be based on subjects “as treated”.

